GetWell Loop is a SaaS platform that allows physicians to monitor signs and symptoms, and communicate with patients during the postoperative recovery process. The platform enables doctors to identify patients at risk of decline in the follow up period. Patients are engaged through mobile and web-based surveys, reminders, and information personalized to the patient's specific condition or treatment plan. The company's platform also collects patients' feedbacks and monitors status against expected progress. Alerts are sent to physicians or providers about patients who are at risk of treatment failures, complications, or hospital readmissions. Physicians are informed if patients are trending toward an adverse outcome based on the patient's responses. Along with helping to prevent readmissions, GetWell Loop can also help institutions collect patient-reported outcomes (PROs) data, which can be used to evaluate and improve quality measures.

GetWell Loop and the Cleveland Clinic are interested in collaborating on a clinical pilot study to demonstrate that high patient engagement leads to enhanced pre-operative preparation potentially reducing length of stay (LOS), readmissions / reoperations, discharge disposition to home rather than another facility, reduced need for in-person follow up, increased patient (and provider) satisfaction, and increased satisfaction survey completion rates after elective primary hip and knee arthroplasty (THA and TKA). These improvements can translate on higher financial savings through the episode especially in light of the alternative payment models.

Specific Aims: GetWell Loop is currently used by orthopedic groups around the country, and is believed to improve peri-operative outcomes after THA and TKA and mitigate risk by: 1. Enhancing patient engagement with providers, 2. Allowing patients to play an integral role in patient-reported outcomes, 3. Generating and relaying actionable pre- and post-operative reporting directly to the clinical team, and 4.

Detecting impending post-operative complications early, enabling timely intervention and preventing avoidable complications and readmissions.

The specific aims of this proposal are to:

- 1. Measure the impact of using GetWell Loop on patient (and provider) satisfaction
- 2. Understand the degree to which high post-operative engagement reduces the need for in-person or telephone follow up appointment time

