 - a. Does the use of GetWell Loop lead to fewer potentially avoidable healthcare utilization encounters such as Emergency Department and hospital visits (including readmissions and reoperations)?
 - b. Does utilizing GetWell Loop improve clinical workflow by minimizing telephone calls and thereby offloading support staff, allowing them to be more efficient?
 - c. Does utilizing GetWell Loop reduce the volume of on call pages by addressing patient questions up front, alleviating concerns, and providing them with the information they need when they need it?
 - d. Does utilizing GetWell Loop allow the practice to identify patients whose inperson follow up needs are minimal, thereby freeing new referrals slots and enhancing same-day access?
 - e. Does GetWell Loop improve the throughput of patients by eliminating unnecessary follow-up appointments?
- 3. Measure length of stay, discharge disposition (home versus extended care facility) and 90 days readmission and reoperation rates
 - a. Does the early detection of adverse signs/symptoms that develop between clinical encounters result in earlier intervention that thereby reduces readmission and reoperations?
 - b. Do Patient Reported Outcomes (PROs), collected at intervals between clinical encounters, provide useful information which facilitates the detections of post-acute complications prior to the next clinical encounter?
 - c. Does patient adherence to instructions as well as recommended activity levels, captured through continuous activity monitoring such as the Jawbone Up Band (a wristband capable of measuring activity), predict time to recovery, functional outcomes, and potential failure rates? (optional)
- 4. Evaluate the financial impact of GetWell Loop in the episode of care

Methods: The study design is a prospective randomized trial in which patients undergoing selected hip and knee orthopedic procedures will be offered peri-operative use of GetWell Loop vs standard care. Approximately 300 patients will be enrolled (150 in each group).

Phase 1: 6 month run-in with 9 month follow (total of 12 month long study). Will collect the following outcome measures:

- Demographics (Age, gender, BMI)
- Comorbidities
- Surgery details (Length of surgery, laterality, surgeon)
- LOS and discharge disposition
- Number/length of follow up visits within 90 days (in person and telephone)
- 90 days readmission and reoperations
- Patient and provider satisfaction survey completion rates

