Physician and staff satisfaction	- Opportunity to demonstrate clinical adoption rates and low barriers to implementation.
Total 90 day post-operative cost from index date+1 (same day) or from index date + LOS (inpatient)*	GetWell Loop templates should be able to either prevent the complication, or through early detection at the clinic level, reduce expense through minimized emergency room visits and readmissions.
*Claims submitted within 90 days must be limited to ICD-10s listed below (or to hospitalization due to ICD-10s below) in order to exclude unrelated claims.	
90 day post-op hospitalization rate (this is a readmission if initially an inpatient procedure, or an admission if initially an outpatient procedure)*	
*Must be associated with ICD-10s listed below in order to exclude unrelated readmissions.	
90-day ED Visit Rate* *Must be associated with ICD-10s listed below in order to exclude unrelated ED visits.	
Number of follow up visits within 90 days	Demonstration to physicians and practices the potential to improve throughput and workflow efficiency by minimizing the number of follow up visits required.
Potentially preventable readmissions	Potentially preventable admissions, events, ED visits. Using an approach similar to 3M's

Potentially Preventable Events grouping software, we will examine all events (ED visits, admissions, complications) for relation to index event, and compare this rate to prior year. Data may be
supplemented by Physician survey.
http://solutions.3m.com/wps/portal/3M/en_US/H ealth-Information-Systems/HIS/Products-and- Services/Products-List-A-Z/PPR-and-PPC-Grouping- Software/

ICD-10 codes for relevant metrics

Description		ICD-10
1.	Must be in 1 st or 2 nd diagnosis and must not be chronic, or	
2.	If patient is admitted, must be in 1 st or 2 nd diagnosis on hospital discharge.	
Infection and inflammatory reaction due to internal prosthetic device, implant, and graft		
•	Due to unspecified implant, device, and graft	T8579XA
•	Due to internal joint prosthesis	T8450XA
•	Due to other internal orthopedic device, implant and graft	T8460XA
Other	complications of internal prosthetic device, implant, and graft	
•	Due to unspecified implant, device, and graft	T859XXA
•	Due to internal joint prosthesis	T8481XA-
•	Due to other internal orthopedic device, implant, and graft	T8486XA; T8489XA; T849XXA
Postoperative infection		K6811
•	Other post-operative infection (abscess, septicemia)	T814XXA
Disrup	tion of wound	

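### Potentially preventable readmissions: events are classified with no masking to arm specified and possible physician-survey input, so the between-arm comparison can be biased in a direction the documents do not settle

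*Combined protocol and SAP*

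**What the plan says.** The Methods section describes a randomized comparison of GetWell Loop with standard care: "Approximately 300 patients will be enrolled (150 in each group"). No blinding of patients, clinicians or assessors is described anywhere in the document.

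The Study Metrics table, in the row on potentially preventable readmissions, says "we will examine all events (ED visits, admissions, complications) for relation to index event", and that the study will "compare this rate to prior year". The method is described as an approach resembling a vendor's "Potentially Preventable Events grouping software". The row adds that data may be "supplemented by Physician survey". It does not say who does the examining, what rule they apply, what they know about the patient's arm, which physicians are surveyed, or what the survey can change.

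The Introduction describes how the platform works: "Physicians are informed if patients are trending toward an adverse outcome based on the patient's responses". Alerts about patients at risk of complications or readmission also go to physicians or providers. No corresponding stream is described for standard care.

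Specific Aim 2a asks whether the platform reduces potentially avoidable emergency and hospital visits. The Data Analysis Plan assigns chi-square tests to categorical outcomes, and t-tests to continuous ones, for every outcome other than the PPE-15 comparison.

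**The concern.** Deciding whether an event is related to the index surgery, or was preventable, leaves room for discretion unless the rule is fixed in advance. Here the rule is only similar to a grouper, so some discretion remains. If the person deciding knows the arm, or can see platform alerts that exist for one arm only, the same event can be labelled differently in the two arms. A physician survey is a second route for the same information, because physicians who received alerts know which of their patients were on the platform. Bad intent is not needed, since the inputs to the decision differ by arm.

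This metric is the plan's most direct measure of the avoidable events in Aim 2a. If labelling differs by arm, the rates can differ when no patient has fared differently, or a real difference can be hidden.

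**Working it through.** The plan gives no figure to reproduce: no event rate, preventable share, alpha or power is stated. The check therefore sets the relevant passages side by side and then gives an illustration whose inputs are assumptions.

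**Side by side**

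| Question | What the document gives |
|---|---|
| Who classifies? | An unnamed "we" (Study Metrics) |
| By what rule? | An approach similar to grouping software; rule not written |
| Masked to arm? | Not stated |
| Other inputs? | Optional physician survey; respondents and role not stated |
| Is arm-specific information in circulation? | Yes: platform alerts to physicians or providers (Introduction) |
| Compared with what? | Prior year (Study Metrics); between arms by implication (Aim 2a, Data Analysis Plan) |

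The fourth and fifth rows together give the mechanism: information that exists for one arm only can reach the classification, and nothing in the plan keeps it out.

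The last row limits its reach. Bias between arms arises only when this rate is compared between arms. The written comparator is "compare this rate to prior year". That does not escape the difficulty. Prior-year patients were not in the trial, so their events carry none of the platform information that the trial generates, and nothing says that the same people would review them by the same rule.

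**Illustration**

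Inputs: 150 per arm (Methods). Assumed: 12 events per arm (12/150 = 8%), at most one per patient; no true difference; 50% labelled preventable in standard care; two-sided 5% test.

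Standard care: 12 × 0.50 = 6.0 events, or 6.0/150 = 4.0%.

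GetWell Loop, by labelled share:

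| Share | Events | Rate | Apparent change | z | Two-sided p |
|---|---|---|---|---|---|
| 40% | 12 × 0.40 = 4.8 | 3.2% | −20% | 0.37 | 0.71 |
| 30% | 12 × 0.30 = 3.6 | 2.4% | −40% | 0.79 | 0.43 |
| 60% | 12 × 0.60 = 7.2 | 4.8% | +20% | −0.34 | 0.74 |
| 70% | 12 × 0.70 = 8.4 | 5.6% | +40% | −0.65 | 0.52 |

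Here z = (p1 − p2) / √[2 p̄(1 − p̄)/150], where p̄ is the mean of the two rates. For the 30% row: p̄ = 0.032; standard error = √(2 × 0.032 × 0.968/150) = 0.0203; z = 0.016/0.0203 = 0.79. The lower two rows show that the same size of labelling difference can work against the platform.

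**If events were commoner**

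With 60% labelled preventable in standard care, 40% in GetWell Loop and no true difference, the chance of a significant result favouring GetWell Loop (normal approximation, 150 per arm) is:

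| True event rate (assumed) | Apparent rates | Chance |
|---|---|---|
| 10% | 6% vs 4% | about 12% |
| 20% | 12% vs 8% | about 21% |
| 30% | 18% vs 12% | about 31% |

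With equal labelling the chance is 2.5%. At low event rates the main harm is a misleading point estimate. A false significant result becomes likelier only if reviewed events are frequent and the labelling gap is wide.

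**The case against.** The strongest reply is that the plan is being read for what it omits. It does not say that classifiers know the arm, or that the surveyed physicians use the platform. It says that data may be supplemented, not that a survey may overturn a classification. A grouper-like approach may be largely algorithmic, and the text speaks of relation to the index event; preventability comes from the row's title and the grouper named. All of this stands. The supportable statement is that masking, rule, assessor and survey role are not specified, and that the arm may be known.

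A reader might also infer that the bias must favour GetWell Loop, on the reasoning that an event occurring despite an alert looks unpreventable. The documents do not support that direction. A documented alert also shows that there was warning, which could make the event look more preventable and count against the platform.

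A reader might further infer a contradiction, because the cost, hospitalization and emergency-visit rows are limited to listed ICD-10 codes and this row is not. That is not an error. A broader grouping beside code-limited rates is a legitimate choice.

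Finally, the metric is one row. It is absent by name from the Phase 1 outcome list and the Schedule of Events. All 90-day readmissions and reoperations, and the code-limited hospitalization and emergency-visit rates, address a similar question with less judgement. This limits the importance of the point but does not remove it: Aim 2a asks about avoidable events, and this row is where the plan tries to identify them.

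**Conclusion.** The concern holds in a limited form. For this metric the plan specifies no masking and no fixed rule, and it allows a physician survey to feed the data while arm-specific alerts are in circulation. Labelling can therefore differ by arm and bias the between-arm comparison, in a direction the documents do not settle. The prior-year comparator written for the row does not avoid this and gives up the protection of randomization.

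The size cannot be estimated from the documents. Under the assumed 12 events per arm, a labelling gap of 10 to 20 percentage points moves the estimate by 20% to 40% in either direction, which is 1.2 to 2.4 events and not significant by itself. The conclusion rests on two readings: that the rate will be compared between arms, as Aim 2a and the general analysis sentence imply, and that those who classify or answer the survey may have access to platform information. The PPE-15 comparison, the only one for which the plan states a superiority test, is unaffected. The change is worth making because it is cheap, and because classification rules are credible only if fixed before the arm is known.

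**What to change.** Amend the row on potentially preventable readmissions and the Data Analysis Plan as follows.

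1. Write one rule for relatedness and preventability, applied identically in both arms, and fix it before any event is reviewed.
2. Have whoever performs the planned review apply it to event listings from which arm, platform alerts and platform messages have been removed, and lock the classifications before the arm is revealed.
3. Keep the physician survey out of the classification and report it separately as opinion.
4. Make randomized standard care the comparator for this metric, and label any prior-year comparison descriptive.

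The cost is plan wording and a little work to redact the listing, which someone outside the review should do because that person will see the arm. Reviewers lose platform context for GetWell Loop events. No extra patients, visits or data collection are needed.
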